## **9. Benefits**

Participants in the CBT-I and SH conditions may benefit from the sleep-related information provided. Participants may also appreciate the opportunity to engage in research that may help others benefit from treatment. Beyond these potential benefits to subjects, this research is expected to inform future research and clinical efforts to treat insomnia and reduce the consequences associated with alcohol use among Veterans. As noted above, we believe the risks of this research to participants are minimal and the overall benefits of this research to subjects and society outweigh these risks.

## **10. Payment and Remuneration**

To enhance follow-up rates, participants will receive up to \$40 for completion of the baseline assessment (\$10 for the in-person assessment, \$10 for completing all seven daily surveys, and \$20 for returning the actiwatch), up to \$50 for the post-treatment assessment (\$40 for assessment, \$10 for all daily surveys), and up to \$60 for the

6-week follow-up (\$50 for assessment, \$10 for all daily surveys), with the potential to earn up to \$150. Participants will also receive reminder texts/calls, have access to free parking, and receive treatment at no cost. Participants who choose not to complete an assessment will not receive payment for that assessment; however, they will be invited to participate in any subsequent assessments (e.g., if they decline the post-treatment assessment, they will still be invited to complete follow-up).

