### 1. Abstract

Alcohol use disorders (AUDs) are prevalent among Veterans and result in significant physical and psychological burden. Among those who receive treatment for AUDs, 1 in 3 relapses to problematic drinking within one year of treatment. Thus, additional strategies are needed to enhance alcohol treatment outcomes. One promising approach involves providing concurrent treatment for a common complaint – difficulty falling or staying asleep. Up to 74% of Veterans seeking treatment for AUD report co-occurring symptoms of insomnia. Given the negative impact of insomnia on attention and emotion regulation, insomnia symptoms may decrease patients' abilities to attend to alcohol treatment and manage negative emotions that lead to craving and relapse. Moreover, approximately 50% of individuals with AUDs report using alcohol to help them sleep, making relapse more likely for those with no other tools or skills to help them sleep. Indeed, sleep disturbance has been identified as a risk factor for relapse among individuals in alcohol treatment. Thus, effective treatment of sleep problems may enhance alcohol treatment. Cognitive Behavioral Therapy for Insomnia (CBT-I) has been effective in reducing insomnia severity in individuals with AUDs; however, no investigations have examined the efficacy of CBT-I delivered concurrently with AUD treatment to determine its impact on treatment outcomes. This R21 aims to examine the feasibility, acceptability, and initial efficacy of a CBT-I supplement to outpatient alcohol treatment. A randomized pilot trial with 80 Veterans who meet diagnostic criteria for AUD and Insomnia Disorder will be conducted. Participants will be randomly assigned to receive Cognitive Behavioral Therapy for Insomnia (CBT-I) or minimal treatment (sleep hygiene handout only; SH) in addition to alcohol treatment as usual. Outcomes will be assessed at the end of the active intervention period (6 weeks) and 6 weeks post-intervention. Outcomes of interest include recruitment/retention rates, treatment satisfaction, insomnia severity, use of alcohol as a sleep aid, percentage of heavy-drinking days, and alcohol-related problems. Analyses will focus on size of treatment effects. This study will provide initial evidence that treatment of insomnia not only improves sleep but also allows participants to derive greater benefit from outpatient alcohol treatment.

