**Baseline assessment.** Participants will provide written informed consent prior to completion of baseline (see Table 1). In the case of remote baseline assessments, an RA will walk the participant through an electronic version of the written consent form, which they will be asked to sign electronically via the Qualtrics platform. The RA will then print and sign the electronic version of the participant's consent. The baseline evaluation will involve assessment of substance use and sleep disorders and full eligibility criteria using the Mini International Neuropsychiatric Interview (MINI) 7.0.2. Consistent with standard practice, those who endorse symptoms of sleep-related breathing disorders, restless legs syndrome, periodic limb movement disorder, or narcolepsy will be referred for polysomnography. Given the prevalence of sleep apnea in this population, individuals who meet all eligibility criteria but report symptoms of sleep apnea will complete one night of holter monitoring (using an Evo Holter Recorder, SpaceLabs Healthcare) at home in their own beds to rule out for sleep apnea.

Eligible participants will complete baseline assessment measures and will be randomly assigned to either the CBT-I or SH condition. Participants in both conditions will be oriented to the prospective sleep diary, which

they will be asked to complete every morning for the next 6 weeks. The RA will provide all participants with a general handout on sleep hygiene (from the National Sleep Foundation website) and answer any questions they may have about the guidelines.

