To confirm diagnosis of insomnia, all eligible participants will complete one week of daily sleep diaries (between baseline and treatment session 1), which will be collected electronically and time-stamped each morning using the Qualtrics data management system. Participants who have not completed the diary each morning by noon will receive a reminder text or phone call from study staff. Sleep diaries measure sleep onset latency, wake after sleep onset, total sleep time, sleep efficiency, and sleep quality. In this study, sleep diaries will also assess use of sleep medication and use of alcohol/other drugs (yes/no) to help with sleep. Sleep medication variables will include name, dosage, and time taken and will be converted to lowest recommended dosage units for data analysis. Participants who are unable to complete the daily sleep diaries by computer or phone will be provided with pen-and-paper surveys to fill out each day by hand.

*Follow-up.* Follow-up assessments (see Table 1) will be administered in person by the RA, who will be blind to participant condition. Upon completion of the study, SH participants will be offered a referral for CBT-I, which is available with trained providers at the VA.

*Remote appointments.* If needed, treatment and follow-up appointments may be completed remotely using Zoom Pro or the VA's Video Connect service. Using their VA email from the VA laptops, research staff would send the participant a link to launch the session. Participants wanting to use their iPhone or iPad for the session would have to download the VA Video Connect application onto their device. On all other devices (e.g., PCs, laptops, Android devices), the participant will simply open the email and click the link to launch the secure video session. This service uses encryption to ensure that sessions are private and secure and is designed for Veterans in rural areas with limited access to healthcare facilities.

*Retention strategies.* To enhance follow-up rates, participants will receive:

- Up to \$40 for baseline (~2hr): \$10 for completing the assessment, \$10 for completing all seven daily surveys, and \$20 for returning the actiwatch.
- Up to \$50 for the post-treatment assessment (~1hr): \$40 for completing the assessment and \$10 for completing all seven daily surveys
- Up to \$60 for the 6-week follow-up (~1hr): \$50 for completing the assessment and \$10 for completing all seven daily surveys

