Use	Construct	Measure(s)	BL	Post	6wk
Cov	Demographics	See instruments	X		
	Other drug use , past 6 weeks	Drug Use Screening Inventory	X	X	X
	Use of sleep medication	Daily Sleep Diary (Carney et al., 2012)	X	X	X
Aim 1	Recruitment	Completion of ≥ 1 session of CBT-I		X	
	Retention	Completion of 6/6 sessions of CBT-I		X	
	Treatment satisfaction , measured separately for CBT-I and CBT-AUD	Client Satisfaction Questionnaire (Larsen et al., 1979)			X
Aim 2	% abstinent days , past 6 weeks	Timeline Follow-back (TLFB) for alcohol (Sobell & Sobell, 1996)	X	X	X
	% heavy-drinking days (≥4/5 drinks/day for women/men)				
	Alcohol problems , past 6 weeks	Short Inventory of Problems ([name] et al., 1995)	X	X	X
	Use of alcohol or other drugs to help with sleep , past 6 weeks	Daily Sleep Diary (Carney et al., 2012)	X	X	X
	Insomnia severity , past 2 weeks	Insomnia Severity Index (Morin et al., 2011)	X	X	X
	Total wake time , average past week	Daily Sleep Diary (Carney et al., 2012)	X	X	X
	Sleep quality , average past week	Daily Sleep Diary (Carney et al., 2012)	X	X	X
	Dysfunctional beliefs, past month	Dysfunctional Beliefs about Sleep Scale	X	X	X
Aim 3	Treatment-related learning	Project SAVE Alcohol Quiz Project SAVE Alcohol Vignette	X	X	X
	Executive functioning	Psychomotor Vigilance Task (Dinges et al., 1985) N-back Task (Schmiedek et al., 2014) Monetary Choice Questionnaire UPPS Measure of Impulsivity Cognitive Failures Questionnaire	X	X	X
	Negative affect , past week	Positive and Negative Affect Schedule	X	X	X
	Emotion regulation , past 30 days	Brief Difficulties in Emotion Regulation Scale (Bjureberg et al., 2016)	X	X	X
	Alcohol craving , past week	Penn Alcohol Craving Scale	X	X	X
	Mental health symptoms	PTSD Checklist for DSM-5 Patient Health Questionnaire-9 for depression GAD-7 measure of anxiety Satisfaction with Life Scale	X	X	X

*Note.* BL=baseline. Cov = potential covariates. Post = post treatment. Wk = week.

*Blinding.* PI [name] will not be blinded to block size or participant assignment because she will inform study therapists of participant assignment to conditions. However, PI [name] and study therapists will be blinded to assessment outcomes, and the assessment RA will be blinded to participant condition.

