## **7. Study Statistics**

*Outcome measures.* Outcome measures are listed in Table 1 above. Primary outcomes include recruitment, retention, and treatment satisfaction (Aim 1) as well as insomnia severity, total wake time, sleep quality, percent days abstinent, percent heavy-drinking days, alcohol problems, and use of alcohol or other drugs as a sleep aid (Aim 2). Secondary (Aim 3) outcomes include treatment-related learning, executive function (attention, working memory, delayed discounting, impulsivity), negative affect, emotion regulation, craving, and mental health symptoms (PTSD, depression, anxiety, life satisfaction).

*Aim 1 analyses.* Recruitment (goal  $\geq 4$  pts/mo) and retention rates ( $\geq 70\%$  complete 5/5 sessions) will indicate feasibility of the intervention. Treatment satisfaction (average score  $\geq 3$ , indicating ‘good’ quality) will serve as an indicator of acceptability. Recruitment, retention, and satisfaction will be measured separately for insomnia and alcohol treatments. We do not expect group differences in recruitment. Descriptive statistics, chi-square, and t-tests will be used to determine between-group differences in retention and satisfaction.

*Aims 2-3 analyses.* Cohen’s  $d$  (adjusted for baseline scores) and 95% CIs will be used to examine the magnitude of between-group differences at post-treatment and 6-week follow-up. We will use HLM to compare conditions at post-treatment and 6 weeks. We chose HLM over other statistical approaches (e.g., ANOVA) because it requires fewer assumptions, has superior ability to handle missing data, and will yield greater

statistical power. In each model, the Level 1 variable will be time. Level 2 portions of the model will include the effect of condition. Hypotheses will be tested by regressing condition on the Level 1 intercept and time effect. Analyses will be intent-to-treat. We will examine whether attrition is associated with any baseline variables and control for such variables when necessary.

*Power analysis.* Post-hoc power analyses conducted in G\*Power 3.0.10 indicate that 80 participants will provide strong power ( $1 - \beta = .99$ ) to detect within-between interactions of moderate magnitude ( $f = .25$ ).

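### Participants who skip the post-treatment assessment can return at follow-up, but a fixed 6-week TLFB window leaves most or all of their treatment-period drinking days uncollected

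*Combined protocol and SAP*

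**What the plan says.** Section 10 (Payment and Remuneration) says that a person who does not complete an assessment forgoes that payment but stays in the study; for example, "if they decline the post-treatment assessment, they will still be invited to complete follow-up".

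Table 2 (section 4) lists the drinking outcomes at baseline, post-treatment and follow-up. The window is written into the outcome label, "abstinent days , past 6 weeks", and the instrument is the "Timeline Follow-back (TLFB) for alcohol". The heavy-drinking row shares that instrument and shows no window of its own, so I read the same window as applying to it. No other source is listed for either outcome. Section 7 names both among the primary Aim 2 outcomes.

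On timing, the Abstract says: "Outcomes will be assessed at the end of the active intervention period (6 weeks) and 6 weeks post-intervention". Table 2 also labels the last visit as six weeks. Table 1 puts post-treatment in week 7 and the last visit in week 12, labelled as one month.

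The diary is the other record of alcohol use during treatment: "sleep diaries will also assess use of sleep medication and use of alcohol/other drugs (yes/no) to help with sleep". Participants are oriented to a diary that "they will be asked to complete every morning for the next 6 weeks", although payment covers only seven-day blocks.

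For missing data, section 7 plans an intent-to-treat HLM with time at Level 1, chosen partly for how it handles missing values, and adds: "We will examine whether attrition is associated with any baseline variables and control for such variables when necessary".

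**The concern.** The TLFB is a day-by-day calendar interview. Someone who missed post-treatment and comes to follow-up is in front of the interviewer and could be asked about the earlier weeks. As written, the interview stops at six weeks back, so their post-treatment value on two primary outcomes stays missing when much of it could be obtained.

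The gap matters because of why the visit may have been missed. The Background describes relapse as common (1 in 3 within a year of treatment). A person could relapse late in treatment, skip the assessment, recover and return at follow-up. Their drinking in the missed interval would then be heavier than their baseline and follow-up values suggest. Attendance could also differ by arm: CBT-I participants come weekly and may have an optional sixth session on the post-treatment date, while SH participants receive a handout. Either mechanism could bias the post-treatment contrast.

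**Working it through.** **Days lost**

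Inputs: baseline in week 1 and post-treatment in week 7 (Table 1); a recall window of 6 × 7 = 42 days (Table 2); follow-up six weeks after post-treatment (Abstract, Table 2) or in week 12, labelled one month (Table 1).

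Count days from baseline = day 0, taking each week at its first day.

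- Post-treatment: (7 − 1) × 7 = day 42. The missed interview would have covered days 0 to 42.
- Follow-up on day F covers days F − 42 to F.
- Days of the missed window recovered = max(0, 84 − F).

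| Reading of follow-up timing | F | Recovered | Lost |
|---|---|---|---|
| Six weeks after post-treatment | 42 + 42 = 84 | 0 | 42 of 42 (100%) |
| Table 1, week 12 | (12 − 1) × 7 = 77 | 7 | 35 of 42 (83%) |
| One month taken as 30 days | 42 + 30 = 72 | 12 | 30 of 42 (71%) |

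Counting only from session 1 in week 2 (day 7), the losses are 35, 28 and 23 of 35 days.

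On the week-12 timing the visits are 77 − 42 = 35 days apart, so even a punctual participant has 42 − 35 = 7 days counted at both time points.

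**Could the diary fill the gap?** No. It records yes or no for alcohol or other drugs used to help with sleep. It gives no drinks per day, so neither percent heavy-drinking days nor percent abstinent days can be scored from it.

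**Number affected.** The documents give no rate of missed post-treatment visits. Recruiting 115 for a final 80 implies a loss of 1 − 80/115 = 30.4%, but does not say how much of that is a missed visit followed by a return. As an assumption, 5% to 30% of 80 is 4 to 24 participants.

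**Power.** Section 7 states power of .99 for a within-between interaction with f = .25 and N = 80. Alpha, the number of measurements m and their correlation ρ are not stated; I assume alpha .05 and sphericity. With two groups, the noncentral F has λ = f²Nm/(1 − ρ), df1 = m − 1 and df2 = (N − 2)(m − 1).

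- N = 80, ρ = .5, m = 2: λ = 0.0625 × 80 × 2/0.5 = 20, power 0.993. With m = 3: λ = 30, power 0.999. The plan's figure is reproduced.
- N = 76 (5% lost, complete cases only), ρ = .5: 0.990 (m = 2), 0.999 (m = 3).
- N = 56 (30% lost), ρ = .5: λ = 14, power 0.957 (m = 2); λ = 21, power 0.987 (m = 3).
- ρ = .3, m = 3 also reproduces the plan (0.989) and falls to 0.938 at N = 56.

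These are pessimistic figures, because the HLM does not drop these participants. The issue is bias more than power.

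**The case against.** The strongest reply is that the planned model already deals with this. A reader might infer from the attrition sentence that adjusting for baseline variables is the plan's only protection. Section 7 does not support that: a likelihood-based HLM keeps these participants and uses their follow-up drinking as well as baseline. That part of the reply stands. What remains is narrower: whether, given those observed values, skipping still depends on drinking in the unrecorded weeks.

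A reader might also infer that treatment-period drinking is never collected. That is exact only on the six-week timing. On Table 1's timing 7 to 12 days are recaptured, and the diary adds some yes/no information.

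A third inference is that people who attend post-treatment late have follow-up days scored as treatment days. The documents give no visit windows or day-scoring rules, so this is possible but not shown.

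There is also a real design argument for a uniform window: everyone recalls the same length of time at every visit. A longer lookback would apply to those who missed a visit, perhaps the heavier drinkers, and could exchange missing values for differential recall error. Table 2's label may also define the outcome period without forbidding a longer calendar. Both points are fair. They call for a sensitivity analysis and an explicit instruction, but do not favour leaving the days uncollected.

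**Conclusion.** The gap is real. Followed as written, the plan leaves 30 to 42 of 42 days (71% to 100%) uncollected on two primary outcomes for anyone who misses post-treatment and returns. This rests on reading Table 2's label as the interview window and on the follow-up timing, which the documents state inconsistently. The post-treatment contrast then relies on a missing-at-random assumption that is open to doubt in this setting.

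The size of the bias cannot be derived. It is tempting to put a number on it: with 10% to 20% missing and 25 points more heavy-drinking days among them, the observed mean would be 0.10 × 25 = 2.5 to 0.20 × 25 = 5 points too low. Neither input comes from the documents, and the shift is in raw means, not in the HLM estimate or the baseline-adjusted Cohen's d. It should not be read as the bias of the planned analysis.

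This is an inexpensive improvement to data collection in a pilot, not a flaw that invalidates the design. Inviting people back is good practice; the fixed lookback limits what the return visit can yield.

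**What to change.** 1. In Table 2, have the post-treatment and follow-up TLFB cover the period since the last completed assessment.
2. Score each day by calendar date into a treatment window and a follow-up window, so a person seen only at the last visit can supply both values and no day counts twice.
3. Flag values recalled over more than six weeks and repeat the analysis without them.
4. Reconcile the follow-up timing (six weeks in the text and Table 2, week 12 or one month in Table 1) so that the two windows are defined.

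The cost is a few more interview minutes for those who missed or delayed a visit, a short scoring rule and one repeat analysis. The downside is longer recall for that subgroup: about 12 weeks on the six-week timing, or 11 on Table 1's.

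The change does not help with people who never return. Nor does it recover other outcomes missed at post-treatment: alcohol problems, which also has a six-week window in Table 2, insomnia severity, or any diary outcomes not completed.

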## **11. Costs**

Participants will be expected to travel to the VA for assessment and therapy appointments. It is unlikely that the expense of this travel will be a burden to participants, as the VA is easily accessible by foot, car, and public transportation. However, participants will be expected to cover the cost of these expenses. Participants will not be charged for other study procedures or for treatment.

## **12. Data Use**

PI [name] will use all project data to oversee project management, treatment, and data analysis. Co-I [name] will access audio data to provide clinical supervision (i.e., feedback on treatment integrity). Co-I [name] will access outcome data for data analysis.

## **13. Software**

The computer program Inquisit will be required for assessments of executive functioning. Funds for Inquisit were included in the NIH application budget; thus, the PI will provide funds for this software. Participants' performance on executive functioning tasks will be saved on the computer's hard drive. However, these data will be tracked using unique participant identification numbers, rather than identifying information. All data will be transferred to the VA secure server as soon as possible.

SPSS will be required for data analysis. The PI was informed that SPSS is available through VINCI.

All software will be approved through the One VA Technical Reference Model for installation and use on the VA network.

## **14. Web applications**

All eligible participants will also complete sleep diaries, which will be collected electronically and time-stamped each morning using the Qualtrics data management system. As a company, Qualtrics is familiar with the nature of academic research and the importance of confidentiality, and their data handling procedures meet strict privacy standards (<https://www.qualtrics.com/privacy-statement/>). All data will be identified using unique participant IDs. The Qualtrics data centers utilize many security measures. Qualtrics' database access is restricted and requires authorization. All computer equipment (servers, SANs, switches, routers, etc.) is redundant and is located in secure, environmentally controlled data centers with 24/7 monitoring. Web traffic does not directly access the database and database requests are reversed proxy via an application server to the database. All information is secured via industry standard firewalls and stringent IT security policies and procedures. Qualtrics utilizes industry standard web application firewalls and DDOS protection. Qualtrics also leverages panel partners who are meticulous in their multiple levels of security, which include redundant data centers, secure servers, encryption which includes one-way encryption, numeric IDs, secure .NET platforms, security clearance, industry standard firewalls, 24/7 monitoring of data centers, confidentiality agreements, and physical, electronic, and managerial procedures. While Qualtrics typically tracks IP addresses as part of its protocol, our research project will opt out of IP address tracking to ensure the survey responses remain confidential. Once downloaded, the data will be stored securely on the VA's network server.

The VA's Video Connect service will be used for remote appointments, if necessary. This service uses encryption to ensure that sessions are private and secure and is designed for Veterans in rural areas with limited access to healthcare facilities. Additionally, Zoom Pro will be an alternate videoconferencing resource for remote appointments. This service has end-to-end encryption and password-protected meetings. Data from these sessions will not be recorded or downloaded.

